5.2.3 Withdrawal Criteria for Second Study Vaccination

Prior to receiving the second vaccination, subjects will be reassessed. If any of these events occur during the study, the subject must not receive the second vaccination but will be encouraged to continue study participation for safety and immunogenicity evaluations through 12 months after the last study vaccination.

The study intervention will be discontinued in a subject for any of the following reasons:

1. Withdrawal of consent.
2. As deemed necessary by the participating site PI or appropriate sub-investigator for non-compliance or other reasons. This may include previously undisclosed or new conditions that meet the exclusion criteria.
3. Any clinically significant medical condition that, in the opinion of the participating site PI or appropriate sub-investigator, poses an additional risk to the subject if he/she continues to participate in the study.
4. Anaphylaxis or unexpected systemic hypersensitivity reaction following the administration of the first study vaccination.
5. Any SAE judged to be related to study vaccine.
6. Pregnancy.
7. Subject is lost to follow-up.
8. New information becomes available that makes further participation unsafe.
9. Termination of the trial.
10. Myocarditis or pericarditis that occurs after the first study vaccination.

5.2.4 Follow-up for Subjects that Discontinued Study Intervention

Discontinuation of study intervention does not require discontinuation from the study, and the remaining study procedures should be completed as indicated by the Schedule of Activities. If a clinically significant finding is identified, including, but not limited to, changes from baseline, after enrollment, the participating site PI or qualified designee will determine if any change in subject management is needed. Any new clinically relevant finding will be reported as an AE.

If the participant is enrolled and seeks vaccination with an EUA/licensed COVID-19 vaccine outside of the study, he/she will be encouraged to discuss this intention proactively with the study investigator and research team and will be able to receive the authorized vaccine at least

one month after the last study vaccination. An unscheduled visit will occur, if possible, prior to the receipt of an EUA/licensed COVID-19 vaccine. The remaining study procedures should be completed as indicated by the Schedule of Activities or the participant will only be followed for safety.

The data to be collected at the time of study intervention discontinuation should include the following:

- Clinical safety laboratory evaluations.
- Complete physical examination (PE).
- Vital signs (BP, pulse, and oral temperature).
- Immunogenicity evaluations.

5.2.5 Study Termination

This study may be prematurely terminated if there is sufficient reasonable cause, including, but not limited to:

- Determination of unexpected, significant, or unacceptable risk to subjects.
- Results of interim analysis.
- Insufficient compliance to protocol requirements.
- Data that are not sufficiently complete and/or not evaluable.
- Regulatory authorities.

If the study is prematurely terminated by the sponsor, any regulatory authority, or the investigator for any reason, the investigator will promptly inform the study subjects and the IRB, as applicable. Study subjects will be contacted, and appropriate follow-up will be conducted, as necessary.

The sponsor will notify regulatory authorities as applicable.

5.2.6 Lost to Follow-up

A subject will be considered lost to follow-up if he or she fails to appear for a follow-up assessment. Extensive effort (i.e., generally three documented contact attempts via telephone calls, e-mails, etc., made on separate occasions) will be made to locate or recall the subject, or at least to determine the subject's health status. These efforts will be documented in the subject's study file.

6 STUDY PROCEDURES

At some participating sites, subjects will be given the option for in-person non-vaccination visits to be conducted in clinic or at home.

6.1 Screening

Screening for this study will be completed through the participating institution's screening protocol or this study's informed consent. Testing will be done according to eligibility criteria and clinical assessment at screening. Screening evaluations for specific eligibility criteria must be completed within 30 days prior to enrollment for the given parameter but may be repeated as needed to confirm eligibility. If consent is obtained, the screening procedures indicated in the Schedule of Activities (see [Table 6](#), [Table 7](#), [Table 8](#), and [Table 9](#)) will be undertaken. To avoid unnecessary additional venipuncture, if the appropriate blood test results for screening are available for the same subject (e.g., recent doctor's visit), these results may be used for assessing eligibility provided the results date is within the 30 days preceding enrolment to this trial.

Abnormal clinical findings from the medical history, physical examination or blood tests at screening will be assessed. Abnormal blood tests following enrollment will be assessed according to the FDA guidance document "Toxicity Grading Scale for Healthy Adult and Adolescent Volunteers Enrolled in Preventive Vaccine Clinical Trials". If a test is deemed clinically significant it may be repeated to ensure it is not a single occurrence. If an abnormal finding is deemed to be clinically significant, the subject will be informed and referred for appropriate medical care with the permission of the subject. Decisions to exclude the subject from enrolling in the trial or to withdraw a subject from the trial will be at the discretion of the Investigator.

Any study subject who has not yet received the current year influenza vaccination may receive this, if available, during the screening period but not within 14 days before or after study treatment start.

6.1.1 Visit 00, Screening, Day -30 to -1, Clinic Visit

- Subjects will be provided with a description of this trial (purpose and study procedures) and asked to read and sign the ICF prior to performing any study procedures.
- Demographic information will be obtained by interview of subjects.
- Eligibility criteria will be reviewed with subjects to ensure eligibility.
- Complete medical history will be obtained by interview of subjects to ensure eligibility.

- All concomitant medications taken within 30 days prior to signing the ICF will be reviewed with subjects to determine stability of chronic diseases and eligibility.
- Vital signs, including oral temperature, pulse, and BP, will be obtained to ensure eligibility. Subjects must not eat or drink anything hot or cold within 10 minutes prior to taking oral temperature.
- Height and weight will be collected for the calculation of BMI.
- A physical examination will be performed on all subjects by a study clinician licensed to make medical diagnoses and listed on the Form FDA 1572 as the site PI or sub-investigator.
- A urine or serum pregnancy test will be performed locally by the site for all women of childbearing potential within 24 hours of vaccination. Results must be negative to ensure eligibility.
- Nasal swab will be collected for SARS-CoV-2 PCR.
- Approximately 17 mL of venous blood will be collected for baseline screening labs including WBC, HgB, PLT, ALT, AST, ALP, T Bili, Cr, CK and PT/PTT.
- Approximately 14 mL of venous blood will be collected for HBsAg, Anti-HCV, SARS-CoV-2 serology (N-specific), and HIV.

6.2 Enrollment

6.2.1 Visit 01, Day 1, Clinic Visit, 1st Study Vaccination (Dose 1)

- Subject's willingness to participate will be reconfirmed and documented in the subject's study records prior to performing any further study procedures, including administration of the first study vaccination.
- Eligibility criteria, including results of the screening labs, will be reviewed with subjects prior to the first study vaccination to ensure eligibility. Subjects who have received approved COVID-19 booster vaccinations are no longer excluded. In addition, subjects with evidence of previous non-acute COVID-19 (serologically positive, but PCR negative) are also no longer excluded.
- Interim medical history, including an assessment for new medical conditions, stability of chronic diseases, will be obtained by interview of subjects prior to the first study

vaccination. Any changes in medical history since the screening visit will be reviewed with subjects prior to the first study vaccination to ensure continued eligibility.

- All concomitant medications (including solicitation for receipt of any non-study vaccines) will be reviewed with subjects prior to the first study vaccination for accuracy and completeness. Any new concomitant medications taken since the screening visit will be reviewed with subjects prior to the first study vaccination to ensure continued eligibility.
- Vital signs, including oral temperature, pulse, and BP, will be obtained prior to the first study vaccination to ensure continued eligibility. Vital signs assessed on Day 1 prior to the first study vaccination will be considered as baseline. Subjects must not eat or drink anything hot or cold within 10 minutes prior to taking oral temperature.
- A targeted physical examination may be performed prior to the first study vaccination, if indicated based on review of complete medical history and any updates obtained by interview of subjects since the screening visit, by a study clinician licensed to make medical diagnoses and listed on the Form FDA 1572 as the site PI or sub-investigator.
- A urine or serum pregnancy test will be performed locally by the site within 24 hours prior to the first study vaccination for all women of childbearing potential. Results must be negative and known prior to enrollment and the first study vaccination.
- A saliva sample will be collected to check for antibodies.
- Approximately 72-80 mL of venous blood will be collected immediately prior to the first study vaccination for baseline cellular immunology assays.
- Approximately 20 mL of venous blood will be collected immediately prior to the first study vaccination for baseline antibody assays. An aliquot may be used as needed to determine pre-vaccination levels of troponins.
- Approximately 32 mL of venous blood will be collected immediately prior to the first study vaccination for peripheral blood mononuclear cell (PBMC) and plasma storage for secondary research.
- Groups 5-15 Only: Approximately 2.5 mL of venous blood will be collected immediately prior to the first study vaccination for baseline transcriptomal analysis and comparisons with post study vaccination transcriptomal signature changes associated with study vaccine reactogenicity and immunogenicity.
- Groups 5-15 Only: Approximately 4 mL of blood will be collected for cytokines.

- Subjects will be enrolled in Advantage *eClinical* and assigned to a treatment arm prior to the first study vaccination.
- Subjects will then receive one 0.25, 0.5, or 1.0 mL dose of study vaccine (depending on treatment assignment) via a single IM injection into the deltoid muscle of the subject's preferred arm. The site of injection (right or left arm) and time of study vaccine administration to the subject will be recorded on the appropriate DCF. Subjects will be observed in the clinic for at least 45 minutes after the first study vaccination. The first study vaccination site will be examined, post-administration reactogenicity assessments will be performed, and any AEs/SAEs/AESIs including PIMMCs/MAAEs/NOCMCs will be recorded on the appropriate DCF prior to discharge from the clinic.
- Subjects will be provided with a Memory Aid and other study-related materials to record daily oral temperature, solicited injection site and systemic reactions, unsolicited AEs, and concomitant medications. Subjects will be encouraged to take their oral temperature around the same time each day. Subjects must not eat or drink anything hot or cold within 10 minutes prior to taking oral temperature. Subjects will be instructed on how to use their Memory Aid and how to measure and record AEs prior to discharge from the clinic. Subjects will be instructed to notify the study center if they develop any severe reactions after the first study vaccination. If the site PI or appropriate sub-investigator deems the reaction severe enough, further instructions will be given to the subject on the proper course of action, including a return to the clinic for immediate evaluation if appropriate.

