Gritstone's heterologous prime-boost vaccines are being developed for the treatment of patients with advanced solid tumors using a SAM vaccine GRT-R902 or GRT-R904 with up to 8 boosts, following a single administration of a ChAd-based prime using either GRT-C901 or GRT-C903. As of April 29, 2021, 48 patients with advanced cancers have been enrolled in phase 1-2 clinical trials and have received a ChAd-based prime vaccine consisting of either GRT-C901 or GRT-C903 at a fixed dose of 1×10^{12} vp followed by up to 8 SAM boosts of either GRT-R902 or GRT-R904 at doses ranging from 30 to 300 µg with at least 9 patients receiving the 300 µg dose as bilateral IM injections. All patients received concomitant doses of intravenous (IV) nivolumab at 480 mg flat dose. A majority of patients also received concomitant doses of ipilimumab subcutaneously at a 30 mg flat dose. No dose-limiting toxicities related to either the ChAd- or SAM-based vaccines in combination with nivolumab and ipilimumab have been observed at the time of this writing. One patient has experienced a serious adverse event (SAE) of treatment-related Grade 2 fever within approximately 12 hours after GRT-C901 and nivolumab, managed with anti-pyretics and fluids and resolved within 24 hours. Most patients reported transient episodes of low-grade fever, injection-site reactions, chills, nausea, fatigue and generally, flu-like symptoms, within 12 to 24 hours after vaccine administration with either the ChAd- or SAM-based vectors. Three patients presented with elevated serum creatine kinase with two patients developing transient signs and symptoms of myositis and rhabdomyolysis. Auto-immune myositis is a known toxicity of nivolumab and/or ipilimumab.

Overall, these symptoms were reversible and generally well tolerated, even in older adult patients with advanced solid tumors. The contribution of nivolumab and ipilimumab to these inflammatory-like responses cannot be excluded. These observations support the administration of the proposed ChAd-based vaccine and SAM-based vaccine encoding antigens of SARS-CoV-2 in healthy subjects at a dose of up to 5×10^{11} vp and 100 µg, respectively.

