3.2 Study Objectives and Endpoints

Table 2: Objectives and Endpoints (Outcome Measures)

Objectives	Endpoints (Outcome Measures)
Primary	

 To assess the safety and tolerability of different doses of ChAd-S or ChAd-S-TCE, and SAM-S or SAM-S-TCE when administered as: 
 prime-boost in healthy naïve adult subjects boost in healthy adult subjects previously vaccinated with an EUA/licensed mRNA or adenoviral-vectorized COVID-19 vaccine 	
 Occurrence of solicited local reactogenicity signs and symptoms for 7 days following each study vaccination Occurrence of solicited systemic reactogenicity signs and symptoms for 7 days following each study vaccination Occurrence of unsolicited AEs for 28 days following each study vaccination Change from baseline for clinical safety laboratory parameters 7 days after each study vaccination Occurrence of SAEs and AESIs, including PIMMCs, MAAEs and NOCMCs, throughout the entire study following the first study vaccination
Secondary	

 To assess the humoral immunogenicity of ChAd-S or ChAd-S-TCE, and SAM-S or SAM-S-TCE 	
 Response rate, and magnitude of SARS-CoV-2-specific antibody binding and neutralization titers (including against emergent viral strains, e.g., B.1.1.7) in serum samples will be assessed via a range of assays measuring total Spike-specific IgG (ELISA-based), and function (neutralization, RBD binding, or similar) in serum on the following days:

Objectives	Endpoints (Outcome Measures)
	
For Stage 1, Groups 1 and 3A: Days 1 and 29 post Dose 1; then Days 29, 181, and 366 post Dose 2
 
For Stage 1, Groups 3B and 4: Days 1, 29, 57, and 85-130 post Dose 1; then Days 15, 29, 85, 181, and 366 post Dose 2
 
For Stage 2, Groups 5-7A*, 7B*, 9, 10A, 10B, and 11A, 11B, and 13-15: Days 1, 15, 29, 85, 181, and 366 post study vaccination
 
For Stage 2, Groups 8A*, 8B* and 12A, 12B: Days 1, 15, 29, and 57 post Dose 1; then Days 15, 29, 85, 181, and 366 post Dose 2

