Subjects will be observed in the clinic for at least 45 minutes after each study vaccination. The study vaccination site will be examined, post-administration reactogenicity assessments will be performed, and any AE/SAEs/AESIs will be assessed and recorded on the appropriate data collection form prior to discharge from the clinic.

All subjects will complete a Memory Aid from Day 1 through Day 8 after each study vaccination. Memory Aids will be reviewed with subjects for AEs (solicited injection site and systemic reactions, as well as unsolicited AEs), SAEs, AESIs, and concomitant medications occurring after each study vaccination. Memory Aid reviews will take place during telephone calls, e-mails, text contacts, or clinic visits on Days 2 and 4 after each study vaccination as well as during clinic visits on Day 8 after each study vaccination.

Reactogenicity assessments will include an assessment of solicited AEs occurring from the time of each study vaccination on Day 1 through Day 8 after each study vaccination, which includes an assessment of injection site reactions including erythema (redness), induration (hardness)/edema (swelling), pain, and tenderness as well as systemic reactions including fever, chills (feverishness), fatigue (tiredness), malaise (general unwell feeling), myalgia (body aches/muscular pain exclusive of the injection site), arthralgia (joint pain exclusive of the injection site), headache, nausea, and diarrhea.

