No formal multiple comparison adjustments will be employed for multiple primary or secondary endpoints. However, multiplicity adjustments will be made for certain primary or secondary endpoint assays, as discussed below, when the assay endpoint is viewed as a collection of hypotheses (e.g., testing multiple pseudo-viruses to determine a positive antiviral functional activity response). Unless otherwise noted, 95% confidence intervals will be calculated. Any statistical tests will be 2-sided and will be considered statistically significant if the p-value is below 0.05.

An SAP will be developed by the SDCC and finalized prior to data lock. Unless specified otherwise in the SAP, missing data will not be imputed.

General Approach

Unless otherwise noted in the SAP, continuous variables will be summarized using the following descriptive statistics: n (non-missing sample size), mean, standard deviation, median, maximum and minimum. The frequency and percentages (based on the non-missing sample size) of

observed levels will be reported for all categorical measures. Unless otherwise specified in the SAP, geometric means of relevant continuous endpoints will be computed as Williams means.

Analysis of the Primary Endpoint(s)

Summaries and analysis of safety data will be presented for the Safety Analysis Population.

Solicited reactogenicity signs and symptoms (local and systemic) will be summarized by severity for each day post study vaccination (Days 1-8) and as the maximum severity over all 7 days.

Additionally, solicited AEs will be analyzed by taking the most severe response over the follow-up period, dichotomizing into a binary variable (none versus mild, moderate, or severe) and using standard techniques, such as exact confidence intervals (CI), to summarize the proportion of subjects reporting each symptom, any application site symptom, and any systemic symptom.

Unsolicited non-serious AEs will be collected from the time of first vaccination through 28 days after each study vaccination. Unsolicited AEs will be coded by MedDRA® for Preferred Term and SOC. All SAEs will be collected from the time of first vaccination through the end of the study. SAEs will be described by detailed listings showing the event description,

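### The diary asks for a routine daily temperature but never for the day's highest value or a reading when feverish, so short fevers can be missed and peak fever grade may be understated

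*Protocol*

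**What the plan says.** **Home measurement.** At the first vaccination visit (Protocol 6.2.1) subjects receive a Memory Aid to "record daily oral temperature, solicited injection site and systemic reactions, unsolicited AEs, and concomitant medications". The next sentence reads "Subjects will be encouraged to take their oral temperature around the same time each day". Both recur at the second-dose visits in 6.3.3, 6.4.5 and 6.6.6. Also in 6.2.1: "Subjects will be instructed on how to use their Memory Aid and how to measure and record AEs prior to discharge from the clinic". What that training covers is not described.

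**Endpoint.** Section 3.2 lists among the primary outcomes "Occurrence of solicited systemic reactogenicity signs and symptoms for 7 days following each study vaccination". Section 7.1 names the "systemic reactions including fever, chills (feverishness), fatigue (tiredness), malaise" and others; fever is one of nine systemic terms in 8.1.1.1.

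**Analysis.** Under 10.5 solicited events are "summarized by severity for each day post study vaccination (Days 1-8) and as the maximum severity over all 7 days". They are also dichotomised as none against any grade, from the most severe response.

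**Decision rules.** In 8.1.6, three or more subjects in a group with a Grade 3 solicited event in the same category prompt review by the Study Steering Committee; no duration is required. In 8.5.1, the sentinel rule needs two subjects with the same Grade 3 solicited event lasting at least 24 hours.

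**Expected fever pattern.** Section 2.3.3 reports that most patients on the sponsor's cancer platform had transient low-grade fever and flu-like symptoms "within 12 to 24 hours after vaccine administration with either the ChAd- or SAM-based vectors", and one Grade 2 fever that resolved within 24 hours.

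**The concern.** The analysis uses a maximum, but the stated measurement is a routine sample. The highest of a set of readings taken at a habitual time cannot exceed the true highest temperature and may fall below it. Thermometer error aside, the discrepancy can only go downward. Other systemic symptoms can be recalled over the whole day, whereas fever is graded from a temperature that someone has to take at the right moment. Chills and malaise are solicited separately and cannot supply a fever grade.

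The stake is the fever line of the primary reactogenicity tables and the one formal rule that counts Grade 3 fevers without a duration condition. With Stage 2 groups of about 7 to 12 (Table 1), one understated grade can turn three qualifying subjects into two. Reactogenicity has already driven the redesign of this trial (2.2, 2.3.3), and 3.1 makes the double-boost dose depend in part on it.

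**Working it through.** **The plan's own figure.** The protocol gives no figure for fever incidence, fever duration or the sensitivity of a daily reading. The nearest figure is Table 4 (10.2): for n = 10 and a true event rate of 20%, the chance of at least one event is 1 − 0.80^10 = 0.893, matching the stated 89.3%. All rows of Table 4 reproduce. The table takes every event that occurs as observed.

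**Capture model (illustrative).** Assume one home reading every 24 hours, a time of day unrelated to the fever, and no other reading. A fever of d hours is then met with probability min(1, d/24), and the apparent rate is the true rate times that probability. The durations are assumptions; the 20% rate is borrowed from Table 4.

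| Assumed d | Capture | Apparent rate if true rate is 20% | Chance of at least 1 recorded fever, n = 10 |
|---|---|---|---|
| 6 h | 0.25 | 5% | 1 − 0.95^10 = 40.1% |
| 12 h | 0.50 | 10% | 1 − 0.90^10 = 65.1% |
| 18 h | 0.75 | 15% | 1 − 0.85^10 = 80.3% |
| 24 h or more | 1.00 | 20% | 1 − 0.80^10 = 89.3% |

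Occurrence is lost only below 24 hours. Peak grade can be understated at any duration, because a reading need not fall on the peak.

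**Escalation criterion.** Suppose exactly three subjects each spend d hours at a Grade 3 temperature, captured independently. All three are recorded with probability (d/24)^3: 0.75^3 = 42% at 18 h, 0.50^3 = 12.5% at 12 h, 0.333^3 = 3.7% at 8 h. Again the durations are assumed.

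**What the model leaves out.**
- Sections 6.5 and 6.6 take oral temperature at every clinic visit, and every Stage 2 group has a Day 2 clinic visit after each dose (6.5.1, 6.6.1, 6.6.7). That is one more time point, so the capture figures are too low for Stage 2.
- In Stage 1, Day 2 contact is remote for Groups 1 and 3A after both doses (6.3.1, 6.3.4) and for Groups 3B and 4 after Dose 1 (6.4.1). Stage 1 enrollment is closed.
- Fever onset is tied to the dose, so reading time and fever are not truly unrelated. Real capture could be higher or lower than d/24.

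**Sentinel rule.** A Grade 3 fever sustained for 24 hours spans at least one daily reading, so its occurrence would be met, although a single reading does not by itself establish the duration.

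**Any systemic symptom.** This proportion changes only for a subject whose fever went unrecorded and who had none of the other eight systemic reactions.

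**The case against.** The text does not say one reading only, does not fix a clock time and does not bar further readings; subjects are merely encouraged. They are trained in measuring and recording events. Section 8.1.4.1 asks for changes in an adverse event's severity to be documented, Memory Aids are reviewed on Days 2, 4 and 8, and severe reactions are to be notified to the site. The Memory Aid and the manual of procedures are not shown and may already ask for more. Reading at a similar time each day is also a sensible standardisation across sequential groups.

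On duration, the 12 to 24 hours in 2.3.3 is time since the dose, not length of fever. The Grade 2 fever that resolved within 24 hours was treated and reported as serious, so it was not missed. The same section gives 24 to 48 hours for reactions to other adenoviral vaccines, in a sentence that goes on to list fever. If that duration applies to fever, no occurrence is lost.

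Much of this stands: it removes any claim to a known size. It does not remove the gap, since none of these provisions tells the subject to take a temperature when feverish or to record the day's highest. Recognising a Grade 3 fever still needs a reading at the right time.

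A reader might go further and infer that the primary endpoint is shown to be biased low, or that higher doses will look better tolerated than they are. The document supports neither. No fever duration is given from which to establish a loss, the method is the same in every group, nothing indicates that capture falls with dose, and no between-group testing is planned (10.1). Nor does escalation hang on a fever count alone: the committee reviews all reactogenicity data, and in Stage 1 escalation was judged unsupported although no halting rule had been met (2.2).

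**Conclusion.** The point holds as a weakness in how fever is ascertained; it is not a contradiction or a numerical error. As written, the protocol allows fevers under 24 hours to go unrecorded and peak fever grade to be understated, with any such error running downward. The exposure lies in the fever rows of the daily and maximum-severity tables and in the Grade 3 count of 8.1.6. The percentages above show sensitivity to an assumed duration and are not estimates for this trial; they rest on a single daily reading and ignore the Day 2 clinic temperature. Because the change is cheap and the measure feeds a primary safety outcome, it should be made. If the Memory Aid or manual of procedures already asks for the highest value or a symptom-triggered reading, the remedy reduces to making the protocol say so.

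**What to change.** Amend the Memory Aid instruction in 6.2.1 and at the second-dose visits still to be conducted:

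1. Keep the routine daily reading around the same time, stored as its own field.
2. Ask for an additional reading whenever the subject feels feverish or has chills.
3. Record the highest temperature of each day in a second field.
4. State in 10.5 that fever severity is graded on the day's highest value, and that the routine reading is used for comparison with groups already enrolled.

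**Cost.** One extra diary and data collection form field per day, and revised subject instructions. The real downside is that ascertainment then differs from earlier groups: fever rates in later groups could look higher for that reason alone. Keeping the routine reading separate allows a like-for-like comparison, and the tables should label which reading each row uses.
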